*Study Design and Methods. Subjects.* Middle-aged and older ART-treated HIV-1-seropositive adults who habitually sleep less than 6.5 hours/night. Baseline Sleep and Circadian Assessments. Baseline PSG assessment will occur in the Sleep and Chronobiology Laboratory to determine sleep EEG staging using a standard 8-hour sleep opportunity at the participant’s preferred bedtime. The baseline PSG recording will also be used to confirm absence of sleep apnea, periodic limb movements, and other sleep disorders. PSG records will be interpreted by a board certified sleep clinician. Participants’ sleep will then be monitored for a week using standardized sleep diaries, wrist actigraphy recorders with concurrent light exposure assessment, and call-ins of bed and wake times to a time stamped voice recorder. This will be followed by a second laboratory visit to assess circadian melatonin phase.

*Individualized Targeted Sleep Intervention.* Older ART-treated HIV-1 infected adults experience a variety of sleep problems. All sleep problems result in sleep deficiency and share features that contribute mechanistically to vascular disease. Our working hypothesis is that regardless of the specific sleep problem, improving sleep will improve vascular endothelial function. We will employ an 8-week individualized targeted sleep intervention. Individualized targeted interventions have the advantage of improving adherence, reducing attrition, and making the strategy personally meaningful. We chose an 8-week duration for the targeted sleep intervention since Cognitive Behavioral Therapy for Insomnia (CBT-I) is a 6-week long treatment and endothelial function has been shown to improve following 4-8 weeks of CPAP treatment for sleep apnea (52, 75, 103).

Participants will be provided all sleep treatments at no cost.

All subjects will be given three brochures published by the American Academy of Sleep Medicine and National Sleep Foundation: one on sleep and health, one on insomnia, and the other on sleep hygiene (Helping Yourself To a Good Night’s Sleep). We will supplement this information with an individualized targeted sleep medicine approach to address individual sleep disturbance profiles. Sleep and circadian expert members of the investigative team will use results from baseline assessments and clinical assessment of sleep disorders to develop the individualized targeted

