We have been successful in modifying sleep duration using similar techniques, thus we are confident in increasing exposure to sunlight using our proposed techniques. Participants will also be instructed to reduce exposure to electrical light after sunset. Investigators will make an initial home visit to measure the light environment and instruct participants on how to reduce the intensity of artificial light exposure (dim TVs, computers and cell phones [e.g., programs such as Flux], home lights—we will provide dimmers and/or fixtures with lower intensity light bulbs to be used at night). When not at home at night, subjects will still be instructed to use light reducing methods on their light emitting technologies. We will use the actiwatch information to ensure subjects are being exposed to less light at night, and we will give feedback.

*Other sleep issues.* Other individual and co-morbid ICSD-3 sleep disorders and factors/physical symptoms commonly associated with HIV that may contribute to sleep disturbance (e.g., night sweats, cough, dyspnea, diarrhea, and pain) will be treated with best clinical practices. We recognize factors, such as ART medications, may contribute to sleep disruption (40, 74, 80) and will include these as covariates in our analysis.

After the 8-week targeted individualized sleep intervention, we will perform follow-up PSG sleep and circadian assessments to objectively quantify improvements in sleep duration and quality and to assess changes in circadian timing relative to sleep. Sleep assessment measures will include:

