Sleep Disorder and Fatigue Questionnaires will be used to describe sleep and any changes pre- post- treatment: PSQI as an indicator of sleep disturbance; ESS as an indicator of excessive daytime sleepiness; ISI as an indicator of the clinical severity of insomnia; Berlin Questionnaire to pre-screen apnea. The cognitive battery of the NIH Toolbox will be used to assess mental processes involved in gaining knowledge and comprehension, such as thinking, knowing, remembering, judging, and problem-solving. The post sleep questionnaire is used after each PSG recorded sleep opportunity to assess subjective sleep latency, sleep quality, number of awakenings, sleep duration, and factors that may have disturbed sleep and a sleepiness rating; the Fatigue Severity Scale (FSS) with modification for HIV patients to quantify self-reported fatigue. These questionnaires have been selected for their sensitivity to sleep problems and treatment.

Ambulatory sleep, light exposure and activity monitoring. Wrist actigraphy with concurrent light exposure (Actiwatch Spectrum; Philips Respironics) will be recorded the baseline week prior to the circadian phase assessment, throughout the 8 week sleep intervention, and the week prior to follow-up circadian and vascular assessments. Participants will also maintain a daily sleep-wake log. All subjects (current and newly enrolled) will receive an instruction sheet on how to use the Actiwatch. Measuring light exposure is critical to assess adherence to circadian light exposure treatment strategies. We have successfully used these methods in many prior studies (8, 59, 117). Actigraphy is a valid and reliable method for estimating

sleep timing and total sleep time (TST). Sleep logs will be used to assess subjective sleep onset latency (SOL) and TST. Our standardized sleep log also includes questions on sleep quality, number of awakenings, daily caffeine and alcohol intake, factors that may have disturbed sleep and a morning sleepiness rating. For descriptive analyses, the average TST for baseline, treatment and follow-up sleep episodes will be calculated based on wrist actigraphy using Actiwatch v.5.57 software (1-minute epochs; medium sensitivity).

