*Statistical Analysis for Specific Aim 3.* The outcome variables FBF responses to acetylcholine (in the absence and presence of L-NMMA and vitamin C), bradykinin (in the absence and presence of vitamin C) and sodium nitroprusside (in the absence and presence of vitamin C) as well t-PA and PAI-1 release in response to bradykinin and sodium nitroprusside (both in the absence and presence of vitamin C) will be measured at baseline and after 8 weeks. To accommodate the longitudinal collection these continuous outcomes will be modeled using linear mixed effects methods as implemented SAS (proc mixed; SAS Institute, Inc., Cary NC). Within-individual difference between measures before and after treatment condition ( $d_i$ ) can be modeled as the primary outcome measure using standard linear regression techniques as described under Aims 1 and 2. Potential confounders such as age, sex, race, family history, BMI, nadir CD4 count, baseline CD4 count, duration of ART and HIV-1 RNA prior to ART will be considered. B-spline transformations to allow for a non-linear relationship will be considered for continuous predictors. Based on available data, literature and clinical input from co-investigators, other potential confounders may also be considered. Potential covariates will be identified using a univariate screen with entry criteria of  $p < 0.25$  and non-significant covariates will be excluded in a backward stepwise approach. The primary analysis will be intention to treat, although a secondary as-treated analysis will be conducted as well. Given the design, treatment conditions and assessment protocols, we anticipate the missing data (due to subject dropout) to be at least missing at random (MAR), if not missing completely at random (MCAR). Assuming missing data that are MAR or MCAR, a "complete case analysis" would yield valid inference. However, this approach would come at a cost of reducing statistical efficiency. Therefore, we will also employ Schafer's multivariate normal imputation approach as implemented in SAS v9.3 (SAS Institute Inc.; *proc MI* - MCMC Method and *proc MIANALYZE*). According to a recent simulation study, this multiple imputation approach generally performed well and "generated more reliable information than complete-case analysis" (<http://www.ncbi.nlm.nih.gov/pubmed/20106935>). Results from the complete-case analysis will be compared with that of the multiple imputation analysis to ensure consistency of the regression parameters.

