*Sample Size Calculations for Specific Aim 3.* Due to the lack of published data regarding the effects of enhancing sleep duration and sleep quality on vascular

endothelial vasodilator and fibrinolytic function in HIV-1-seropositive adults, sample sizes for the targeted sleep intervention were determined based on data from the P.I.s laboratory in HIV-1 adults and published studies on comparable lifestyle intervention (e.g. exercise) effects on nitric oxide-mediated endothelium-dependent vasodilation and endothelial t-PA release in middle-aged and older adults (30, 93, 109). The average magnitude of change in FBF response to acetylcholine was ~30% and a change in t-PA release of ~35%. Corresponding effect sizes were 0.71-1.25. Sample sizes were calculated based on 80% power at an alpha level of 0.05. A sample size of 23 subjects is required to detect this physiologically meaningful change. To facilitate equal gender distribution a sample size of 24 subjects should be sufficient to show significant changes if present. This sample size also allows for detection of a correlation coefficient of 0.35 with greater than 80% power at an alpha level of 0.05 (95). To account for an estimated ~20% dropout rate from the intervention, we will enroll 30 subjects.

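### Aim 3 has no prespecified analysis of whether vascular change tracks sleep change, although the data for one are already to be collected

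*Combined protocol and SAP*

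**What the plan says.** **Hypothesis.** Under Individualized Targeted Sleep Intervention, the working hypothesis is that "regardless of the specific sleep problem, improving sleep will improve vascular endothelial function".

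**Model.** Under Statistical Analysis for Specific Aim 3, vascular outcomes at baseline and eight weeks go into a linear mixed model, and the within-person difference d_i "can be modeled as the primary outcome measure using standard linear regression techniques as described under Aims 1 and 2". The named covariates are "Potential confounders such as age, sex, race, family history, BMI, nadir CD4 count, baseline CD4 count, duration of ART and HIV-1 RNA prior to ART": nine candidates, none of them a sleep variable. The list is open, since "other potential confounders may also be considered". The paragraph on other sleep issues adds: "We recognize factors, such as ART medications, may contribute to sleep disruption (40, 74, 80) and will include these as covariates in our analysis". Those are causes of poor sleep, not the change in sleep.

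**Role of the sleep data.** Under Ambulatory sleep, light exposure and activity monitoring: "For descriptive analyses, the average TST for baseline, treatment and follow-up sleep episodes will be calculated based on wrist actigraphy". The questionnaires and the PSG scoring are likewise given the task of describing sleep and how it changed.

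**Nearest approaches to a link.** The Phase I section on ambulatory monitoring between Visits 2 and 3 does plan to relate sleep to vascular outcomes, but with Phase I data only. Sample Size Calculations for Specific Aim 3 says "This sample size also allows for detection of a correlation coefficient of 0.35" with more than 80% power. It names neither variable, and the Aim 3 analysis section contains no correlation.

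**The concern.** The hypothesis is about a path: the intervention improves sleep, and improved sleep improves vascular function. The analysis examines only the end of that path, the mean vascular change, and the sleep data are summarised separately.

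This matters more than usual because Aim 3 is one group measured twice. An active control is mentioned in passing in the weight-maintenance paragraph, but no control arm appears in the Aim 3 design, analysis or sample size. Parts of the programme could affect the vasculature by routes other than sleep, such as CPAP, zolpidem, added daylight and morning walks, and bi-weekly contact with nutrition and exercise staff. Whether larger sleep gains go with larger vascular gains is one of the few pieces of within-study evidence on the stated mechanism.

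Leaving the analysis unspecified also leaves a wide later choice: TST, PSG, PSQI, ISI or ESS, each against many vascular endpoints.

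**Working it through.** **1. Does any planned Aim 3 analysis use sleep change?**

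- Mixed model or regression on d_i: no sleep term is named.
- Open covariate clause: it admits confounders. Sleep change is the proposed mediator, and possible entry through a p < 0.25 screen with backward elimination is not a prespecified test.
- As-treated analysis: planned, but not defined by sleep gained.
- Phase I association: cross-sectional, and separate from the Phase II change.
- Correlation of 0.35: no variables and no matching analysis.

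The answer is no.

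**2. The plan's own correlation figure.** Inputs from the Aim 3 sample-size section: r = 0.35, n = 24, alpha 0.05, power above 80%. Sidedness is not stated, so both versions are shown. By Fisher's z, power = Φ(atanh(r)·√(n − 3) − z).

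- atanh(0.35) = 0.3654 and √21 = 4.583; the product is 1.675.
- Two-sided: Φ(1.675 − 1.960) = Φ(−0.285) = 38.8%. Simulating the t test for r gives 39.7%.
- One-sided: Φ(1.675 − 1.645) = Φ(0.030) = 51.2%.

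The stated figure does not reproduce. Smallest r with 80% power, two-sided: tanh((1.960 + 0.842)/4.583) = tanh(0.611) = 0.545 (one-sided 0.495). Completers needed for r = 0.35: (2.802/0.3654)² + 3 = 61.8, so 62 (one-sided 50). If all 30 enrolled subjects completed, power at r = 0.35 would be 47.6% and the smallest r 0.492, two-sided.

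**3. What 24 completers can estimate.** 95% CI = tanh(atanh(r) ± 1.960/√21), a half-width of 0.428 on the z scale.

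| Observed r | atanh(r) | 95% CI |
|---|---|---|
| 0.5 | 0.549 | 0.12 to 0.75 |
| 0.7 | 0.867 | 0.41 to 0.86 |

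A strong association is estimable, a moderate one only loosely.

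**4. The pre-post test.** Take the low-end effect size of 0.71 as mean change divided by its SD (assumption). A two-sided paired t test with 24 subjects then has 91.5% power. The statistic contains no sleep term, so its power is the same whether or not vascular change is correlated with sleep change; simulation with zero correlation gives 91.3%. This is ordinary power given a real vascular change. With no vascular change the rate is 5%.

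**5. Fitted vascular change at zero sleep change.** Suppose the whole effect runs through sleep, and the measured sleep change has reliability λ. The fitted slope shrinks by the factor λ, so the fitted value at zero sleep change is (1 − λ) times the mean vascular change. For λ from 0.5 to 0.8 (assumption), 50% to 20% of the effect appears to occur without sleep change. This quantity would mislead.

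**The case against.** The strongest reply is that the pre-post test is the right test for the aim as stated. Aim 3 and the Experimental Design section ask whether the intervention improves vascular function, and an intention-to-treat comparison of before and after addresses that. The mechanism is only a working hypothesis. This stands: the missing analysis is a secondary one.

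A reader might infer that Aim 3 could be declared positive with nobody knowing whether anyone slept better. The documents do not support that. Follow-up PSG and circadian assessments are meant to quantify sleep improvement objectively, questionnaires and actigraphy are compared before and after, and CPAP use is monitored. If sleep did not change, the report would show it. Weight and activity, two rival explanations, are also controlled.

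A reader might take the 91.5% as the chance of a false attribution to sleep. It is not; it presupposes a 0.71 SD vascular change and would be the same with the extra analysis in place.

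A reader might also hold that attribution to sleep should require a positive slope. At n = 24 that rule is unsound. A true association below about 0.55 would have less than 80% power, and if subjects gain similar amounts of sleep the slope is poorly determined even when sleep causes all the benefit.

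Finally, assigning average TST to description states one use and does not bar others, and the correlation sentence suggests that some association was intended. Both are fair, but neither specifies an analysis.

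**Conclusion.** The point holds as a cheap improvement. The plan hypothesises that better sleep drives vascular improvement, includes no sleep variable in the Aim 3 models, gives Phase II sleep measures a descriptive role, and so has no prespecified analysis of whether vascular change tracks sleep change. The absence follows from the text and needs no assumption.

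The likely gain is modest. The analysis would be observational and imprecise, able to show a strong association and likely to be inconclusive on a moderate one. The precision figures assume 24 completers, approximate bivariate normality and, where marked, two-sided 5% tests. The documents do not support calling the primary Aim 3 test invalid, or saying that sleep change will go unreported.

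**What to change.** In Statistical Analysis for Specific Aim 3, add one named secondary, exploratory analysis:

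- **Outcomes:** d_i for the acetylcholine FBF response and for the bradykinin t-PA response, using the same dose-response summary as the main Aim 3 analysis.
- **Predictor:** each subject's change in weekly mean actigraphic TST, follow-up Days 2-8 minus baseline Days 2-8.
- **Companion predictor:** one pre-named sleep-quality change, for example PSQI, because the plan's CBT-I works partly by reducing time in bed, so benefit need not appear as longer sleep.
- **Reporting:** slopes or correlations with 95% CIs, beside the mean sleep change. Treat the four comparisons (two outcomes by two sleep measures) as estimates, without significance claims.
- **Interpretation:** state that a wide interval is inconclusive. Do not make attribution conditional on the slope, and do not rely on the fitted change at zero sleep change.

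In the ambulatory-monitoring paragraph, say that actigraphic TST serves this analysis as well as description. If the correlation sentence in the sample-size section is tied to it, restate the figure: with 24 completers, about 39% power two-sided for r = 0.35, and 80% power only for r of about 0.55.

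The cost is a few lines of text, with no new visit or measurement. The downside is a wide interval and an association that cannot by itself establish cause.

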*Intra-Arterial Administration of Vitamin C:* After allowing sufficient time (45 minutes) for FBF to return to baseline following the infusions of acetylcholine + L-NMMA, vitamin C will be infused at a constant rate (12 mg/100 mL tissue/min) for 5 minutes. This vitamin C concentration has been shown to both protect human plasma from free radical-mediated lipid peroxidation (37) and improve endothelium-dependent vasodilation and endothelial t-PA release in conditions associated with oxidative stress (79, 97, 101, 106). Vitamin C infusion will be maintained at the same rate while the bradykinin, sodium nitroprusside and acetylcholine dose-response curves are repeated in the same order as performed earlier. Net endothelial release rates of t-PA and PAI-1 (antigen and activity) will be determined at time 0 and 5 minutes of vitamin C infusion and after each dose of bradykinin and sodium nitroprusside in the presence of vitamin C. A 15-minute washout period will be provided between each dose (106).

*Statistical Analysis for Specific Aims 1 and 2.* For Aims 1 and 2 we will deploy standard linear regression techniques to evaluate whether chronic insufficient sleep is associated with (Aim 1) endothelium-dependent nitric oxide-mediated vasodilation and (Aim 2) vascular endothelium capacity to release tissue-type plasminogen activator. In both scenarios, the continuous vascular measures from Aim 1 and Aim 2 will be modeled as dependent variables in separate linear regression procedures. Independent variables for these models will include the primary variable of interest - insufficient sleep - as well as other important covariates including age, sex, race, BMI, CD4 count, and duration of ART. The primary test of the hypothesis will focus on the parameter estimate for insufficient sleep for both models under Aims 1 and 2.

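### Aim 3 selects covariates on the same 24 or so subjects it tests; this makes the change-score regression modestly anti-conservative, and the plan leaves its primary model unsettled

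*Combined protocol and SAP*

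**What the plan says.** The section Statistical Analysis for Specific Aim 3 first assigns the outcomes to linear mixed models. It then says that the within-person difference d_i "can be modeled as the primary outcome measure using standard linear regression techniques as described under Aims 1 and 2". The section for Aims 1 and 2, to which this points, states: "The primary test of the hypothesis will focus on the parameter estimate for insufficient sleep for both models under Aims 1 and 2". No test parameter is named for Aim 3.

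Nine potential confounders are listed: age, sex, race, family history, BMI, nadir and baseline CD4, time on ART and pre-treatment viral load. Further confounders and B-splines may be considered, and the paragraph on other sleep issues adds ART medications. Candidates pass a univariate screen at p<0.25, and then "non-significant covariates will be excluded in a backward stepwise approach". Neither the level for staying in the model nor any centring is stated.

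On size, the plan says "a sample size of 24 subjects should be sufficient to show significant changes if present" and "To account for an estimated ~20% dropout rate from the intervention, we will enroll 30 subjects". The Aim 3 strategy and methods describe one group of short sleepers, all offered the intervention.

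**The concern.** A covariate that survives screening and elimination does so partly because it happens to fit the observed change scores. The residual variance is then too small, and the usual standard error treats the chosen model as if it had been fixed in advance. With few subjects and many candidates, p-values come out too small and intervals too short.

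Nothing is gained in exchange. Each person is their own control, so a characteristic that does not change over the eight weeks cannot confound the average within-person change. Because Aim 3 has many outcomes, each could also end with a different covariate set.

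**Working it through.** **The plan's sample size.** Inputs from Sample Size Calculations for Specific Aim 3: "Sample sizes were calculated based on 80% power at an alpha level of 0.05"; "Corresponding effect sizes were 0.71-1.25"; "A sample size of 23 subjects is required to detect this physiologically meaningful change". Sidedness is not stated; two-sided is assumed.
- Normal approximation at 0.71: ((1.960 + 0.842)/0.71)² = 15.6, so 16. The exact paired t-test needs 18.
- The stated 23 matches 0.71 at 90% power (exact power 0.902), or an effect of about 0.61 at 80%. It does not follow from the stated inputs if 0.71 is in units of the SD of change, but the difference is conservative.
- Dropout: 24/(1 − 0.20) = 30, as stated. The checks below use n = 24, and n = 30 for comparison.

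**Change regression, centred covariates.** Model: d_i = α + Σβ_j(x_ij − x̄_j) + e_i.
- The estimate of α is the mean of d_i, whichever covariates are kept.
- SE(α) = s_res/√n, with s_res² = RSS/(n − 1 − q) for q kept covariates.
- Selection therefore cannot move the estimate. It can only change the error bar, and it favours covariates that lower s_res by chance.

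**Simulation.** True mean change zero, normal errors, independent pure-noise covariates, screen at p<0.25, backward elimination, two-sided 5% test of α; 6,000 runs per setting (Monte Carlo SE about 0.3 points). Cells show type I error, then mean interval width relative to the unadjusted interval.

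| n | Candidate columns | Stay 0.05 | Stay 0.10 | Stay 0.25 |
|---|---|---|---|---|
| 24 | 9 | 6.6%, 0.95 | 6.9%, 0.93 | 7.7%, 0.91 |
| 24 | 12 | 7.3%, 0.93 | 8.2%, 0.90 | 8.2%, 0.89 |
| 24 | 20 | 9.0%, 0.87 | 10.5%, 0.84 | 11.1%, 0.82 |
| 30 | 9 | 6.7%, 0.96 | 5.6%, 0.94 | 7.3%, 0.93 |

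- In the same runs at n = 24 the unadjusted paired test gave 4.8-5.5%. Keeping all nine covariates without selection gave 4.7-5.4%. The excess therefore comes from selection.
- The 5.6% at n = 30 should be read against 4.2% for the unadjusted test in that run.
- Separate runs with 18 candidates at stay level 0.05 gave 8.1-8.6%, with intervals 11-12% narrower.
- With nine noise candidates at stay level 0.05, at least one was kept in 38% of trials.
- Correlation of 0.3 among the covariates gave 6.2%.

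**Mixed model.** Write y_it = μ + τt + Σβ_j x_ij + b_i + e_it, with t = 0 before and 1 after. Subtracting within person gives d_i = τ + (e_i1 − e_i0): the covariates and the person effect cancel. In a numerical check with complete pairs, the time effect was 0.4566 with SE 0.2061 with 0, 1 or 3 covariates, equal to the paired test.

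**Uncentred covariates.** The intercept becomes mean(d) − Σβ_j x̄_j, the predicted change for someone whose kept covariates are all zero. Age is restricted to 40-75, so zero is far outside the data. That intercept is not the mean change.

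**The case against.** The strongest reply is that the plan names the mixed model first, and there the selection does no harm when pairs are complete. This stands, and it limits the point. A reader might infer that the primary Aim 3 p-values are too optimistic whatever model is used; the documents do not support that. They do, however, offer the change score as a possible primary outcome and never choose between the two.

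Second, the inflation is small for the nine named covariates. That is also right. The larger figures need splines or added candidates, which the plan allows without giving a number.

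Third, a reader might quote a far larger error rate from uncentred covariates. Simulated values ran from 11% to 34%, depending on how far the covariate means were assumed to lie from zero. The plan never says it will test such an intercept, and at means 2 and 5 SD from zero the interval was 1.5 and 2.8 times wider, not narrower. This is a reason to state centring, not a measure of the plan's error rate.

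Fourth, a reader might infer that Aim 3 would test an insufficient-sleep term that cannot be estimated, since every Phase II subject is a short sleeper. The cross-reference is to regression techniques and does not carry that parameter over. What stands is that the Aim 3 parameter is unstated.

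Fifth, covariates may have other uses. The paragraph on keeping body weight stable mentions an active control intervention, and in a comparison of groups covariates could matter. No control arm is described or sized, but the wording is there. Baseline covariates can also support the missing-at-random assumption. Both replies stand.

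**Conclusion.** The point holds for the change-score regression. With about 24 subjects and centred covariates, the stated selection rule gives a true type I error of about 6-8% for a nominal 5% with the nine named candidates, and about 8-11% with 18-20 columns. Intervals are about 5-9% and 11-18% too narrow respectively. It does not hold for the mixed-model time effect with complete pairs and main-effect covariates.

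The statement that covariates remove no confounding rests on the single-arm design in the Aim 3 strategy and methods. The figures assume normal errors, independent noise covariates and a stay level between 0.05 and 0.25. A covariate that truly predicts change does not rescue the rule: with a coefficient of 0.5 residual SD, one run gave 8.7% after selection against 4.8% unadjusted. This is a modest flaw that should be corrected, not one that undermines the aim.

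**What to change.** - Name one primary Aim 3 test: the post-minus-pre time effect in the mixed model, or equivalently with complete pairs the mean of d_i. If covariates are wanted in the d_i regression, pre-specify a short set, centre each at its mean, and test the intercept.
- Delete the p<0.25 screen and backward elimination from the primary analysis. Label any selected-covariate model exploratory, as a description of who responds.
- Baseline covariates may stay in the imputation model to support missing at random.
- Reconcile the active-control wording with the single-arm design.

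The cost is SAP wording. Some precision is lost if an omitted covariate truly predicts change. That gain is partly conditional: a centred fit treats this sample's covariate means as fixed, and in the run with a real predictor, keeping all nine covariates without selection still gave 7.2% when subjects were treated as a random sample. That argues for keeping any pre-specified set short.

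### With 24 subjects, power to detect a correlation of 0.35 is about 39% (two-sided), not above 80% as the Aim 3 sample size section states

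*Combined protocol and SAP*

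**What the plan says.** The statement is in section I of the combined protocol and SAP, under Sample Size Calculations for Specific Aim 3. The paragraph bases the sample size on the pre-post change in the vascular outcomes: "A sample size of 23 subjects is required to detect this physiologically meaningful change". It then rounds up: "To facilitate equal gender distribution a sample size of 24 subjects should be sufficient to show significant changes if present". The next sentence makes a second claim for the same number, that it "allows for detection of a correlation coefficient of 0.35 with greater than 80% power at an alpha level of 0.05". A statistics textbook is cited for it. Enrolment comes last: "To account for an estimated ~20% dropout rate from the intervention, we will enroll 30 subjects".

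The paragraph names neither the two variables to be correlated nor whether the test is one- or two-sided. Statistical Analysis for Specific Aim 3 describes mixed models and says that the within-person change "can be modeled as the primary outcome measure using standard linear regression techniques as described under Aims 1 and 2". It describes no correlation analysis.

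**The concern.** A correlation of 0.35 is modest and 24 is a small sample, so power above 80% is implausible on sight. A quick check supports the doubt. If a sample correlation of 0.35 would not itself be significant at n = 24, then a true correlation of 0.35 will be detected less than about half the time.

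What is at stake is how any Aim 3 correlation would be read. Phase II collects actigraphy, polysomnography and melatonin phase alongside the vascular outcomes, so relating change in sleep to change in vascular function would be a natural use of the data. Someone who trusts the stated power could take a null correlation in 24 people as evidence of no association.

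**Working it through.** **Inputs.** All come from the Aim 3 sample size paragraph: n = 24 (also 23 and 30), r = 0.35, alpha = 0.05, claimed power above 80%. Sidedness is not stated, so both are shown.

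**Formula.** For a test of zero correlation by Fisher's z, power is approximately Φ(atanh(r)·√(n − 3) − z_crit). The two-sided test adds the negligible opposite tail. z_crit is 1.960 two-sided and 1.645 one-sided.

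**Attempt to reproduce the plan's figure at n = 24.**

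- atanh(0.35) = 0.3654 and √21 = 4.583, so the product is 1.675.
- Two-sided: Φ(1.675 − 1.960) = Φ(−0.285), giving 38.8%.
- One-sided: Φ(1.675 − 1.645) = Φ(0.030), giving 51.2%.

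The claimed figure is not reproduced. Two other methods were run for each Aim 3 headcount: the noncentral t formula, which treats the predictor as fixed, and simulation of bivariate normal data with the t test of r.

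| n | Fisher z, two- / one-sided | Noncentral t, two- / one-sided | Simulation, two- / one-sided |
|---|---|---|---|
| 23 | 37.2% / 49.6% | 40.1% / 53.5% | 38.4% / 51.4% |
| 24 | 38.8% / 51.2% | 41.7% / 55.1% | 39.9% / 52.8% |
| 30 | 47.6% / 60.0% | 50.6% / 63.7% | 48.5% / 61.4% |

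No cell reaches 80%.

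**Sample size for 80% power at r = 0.35.** n = 3 + ((z_crit + 0.842)/0.3654)².

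- Two-sided: 61.8, so 62 (59 by noncentral t).
- One-sided: 49.3, so 50 (46 by noncentral t).

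**Correlation detectable with 80% power at n = 24.** r = tanh((z_crit + 0.842)/√21).

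- Two-sided: tanh(2.802/4.583) = 0.545.
- One-sided: 0.495.

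**Check without a power formula.** At n = 24 the two-sided 5% critical value of |r| is 0.404. An observed r of exactly 0.35 gives t = 0.35·√22/√(1 − 0.35²) = 1.752 on 22 df, p = 0.094, which is not significant.

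**Does the error reach the main Aim 3 sample size?** It does not. The lowest effect size in the paragraph is 0.71. If that is the mean change divided by the standard deviation of the changes, a paired t test needs 18 subjects for 80% power and 23 for 90%, so 24 is adequate. The dropout allowance is also right: 24/(1 − 0.20) = 30.

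**The case against.** The strongest reply is that little depends on the sentence. It sets no sample size, names no variables and supports no analysis in the Aim 3 statistical section. That stands, and it limits the consequence; it does not make the figure true.

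A second reply is that 39% is the lowest of the available estimates and that sidedness is unstated. Across methods the range at n = 24 is about 39% to 42% two-sided and 51% to 55% one-sided. One-sided, the chance of missing a true 0.35 is nearer one in two than six in ten. This is fair on precision, but the whole range lies well below 80%.

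A third reply is that the authors may have had another sample or quantity in mind, since the derivation is not shown. The candidates are:

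- **Phase I total of 56.** The Phase I section on ambulatory sleep monitoring does plan to relate sleep to vascular outcomes. Power there is 76% two-sided and 85% one-sided by Fisher z.
- **Two assessments per subject pooled as 48 observations.** This gives 69% two-sided and 79% one-sided by Fisher z (82% one-sided by noncentral t), and it ignores the dependence within subjects.
- **0.35 meant as r².** Then r = 0.59 and power at n = 24 is 88% two-sided.

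The text supports none of these. The sentence speaks of a correlation coefficient and follows directly on 24 subjects, and the first two readings pass 80% only one-sided. They are a reason to ask the authors what was intended.

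**Conclusion.** The stated power is wrong. At the sample size named, power for a correlation of 0.35 falls about 40 percentage points short of the claim two-sided (38.8% by Fisher z) and almost 30 points short one-sided (51.2%). Full retention of all 30 enrolled subjects does not rescue it. The calculation assumes roughly bivariate normal data, one independent pair of values per subject and a test of zero correlation at alpha 0.05. The choice of approximation moves the n = 24 result by no more than about 4 points.

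This is a definite error in a formal power statement and should be corrected. It is confined to a secondary claim: the pre-post comparison and the numbers 23, 24 and 30 do not rest on it.

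**What to change.** Replace the sentence with wording such as: *With 24 completers the study has 80% power (two-sided alpha 0.05) to detect a correlation of about 0.55; power for a correlation of 0.35 is about 39%.* Name the two variables. If a one-sided test was intended, say so and give about 0.49 and 51% instead. If another sample was meant, state it and recompute.

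Deleting the sentence is equally acceptable, since no Aim 3 correlation analysis is specified. Any correlation later reported from Aim 3 is best labelled exploratory and given with its confidence interval.

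The cost is one sentence and a less favourable stated detectable correlation. Sample size, design and primary analysis stay as they are.
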